## 1.2 Study design

This is a Phase IV, multicenter, randomized, double-blind, placebo-controlled, parallel-group study evaluating the effect of Acclidinium Bromide (a long-acting muscarinic antagonist delivered by the Pressair® dry powder inhalation [DPI] device) compared with placebo on long-term CV safety and COPD exacerbations in outpatients at least 40 years of age who have been diagnosed with moderate to very severe COPD (postbronchodilator % predicted forced expiratory volume in 1 second [FEV1] < 80% and FEV1/forced vital capacity [FVC] ratio < 70%) and a history of CV or cerebrovascular disease and/or significant CV risk factors.

Note: in this document

1. The term “double-blind treatment period” applies to the following 2 scenarios:
  - When used in “maximum of 36-months double-blind treatment period”
  - When used for patients who completed 36-months treatment (completer)
2. The term “during the treatment period” refers to on-treatment period.
3. The term “during the whole study period” refers to both on-treatment and off-treatment (post-treatment follow-up) periods.

The study consists of two-week washout/run-in period (for patients on a long-acting muscarinic antagonist [LAMA]) followed by a maximum of 36-month double-blind treatment period.

Signed informed consent form (ICF) from the patient or the patient’s legally authorized representative will be obtained before any study-related procedures are begun. All patients will be assigned a patient identification (PID) number via the interactive web response system (IWRS). Patients meeting the entry criteria for this study will be randomized (1:1) to acclidinium bromide 400 µg (abbreviated as acclidinium hereafter) twice a day (BID) or placebo BID. This study will conclude when 122 patients have experienced an adjudicated MACE.

Patients who prematurely discontinue investigational product (IP) will participate in a post-treatment follow-up period. The follow-up period will include on-site visits and telephone visits to collect MACE, COPD exacerbations, concomitant medications, and SAEs for the remainder of the study duration.

An independent Data Safety Monitoring Board (DSMB) will be established for this study. The DSMB will periodically monitor and review relevant clinical safety data, including adjudicated MACE.

Patients will be assessed according to the Schedule of Evaluations (See Section 2 of the clinical study protocol [CSP]).

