## **1.3 Number of subjects**

### **1.3.1 Power for the primary safety endpoint: time to first MACE event**

For this study, a total of 122 patients with MACE will be needed to have 90% power, at 5% significance level, to rule out a hazard ratio of 1.8 in time to first MACE in acclidinium bromide treated patients relative to placebo, assuming the hazard rate is 1.0 under the alternative hypothesis. The justification for the hazard ratio of margin of 1.8 is provided in Appendix IV of the CSP.

This ASCENT COPD study will be recruiting patients with a FEV1 below 80% and a planned maximum of 36 months double-blind treatment period. The assumption of 1.9 MACE per 100 patient years would be reasonable for this study (See Section 9.7.9.1 of the CSP for details). To obtain 122 MACE in this study with 1.9 MACE per 100 patient years of treatment, a total of 6,500 patient years of treatment (aclidinium bromide and placebo) would be needed. Assuming a treatment discontinuation rate of 40% and a study discontinuation rate of 20% at year 2, and following an exponential distributions for time to events and time to discontinuations, a sample size of 4000 is needed to ensure 90% power to observe 122 events applying the on-study analysis, and an 80% power to observe 91 events applying the on-treatment analysis.

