### **1.3.2 Power for the primary efficacy endpoint: rate of moderate or severe exacerbations per patient per year during the first year of treatment**

The sample size of 4,000 patients after 1 year of treatment will have ~89% power to detect a reduction in the rate of moderate or severe COPD exacerbations per patient per year during the first year of treatment of 14% (rate ratio of 0.86 in acclidinium bromide relative to placebo) at 0.05 significance level. The 89% power was calculated assuming a treatment discontinuation rate of 30% during the first year, a placebo rate of 0.8 exacerbation per patient per year (reduced from 1 to 0.8 as not all patients will have a history of exacerbation prior to randomization), and an overdispersion factor  $k$  of 0.67 (Keene et al, 2007).

See Section 9.7.9 of the CSP for detailed information on determination of sample size and power calculation.

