#### **3.4.2 Spirometry outcome variable**

- Change from baseline in morning pre-dose trough FEV1 at visits 2, 3, 4, 5, 6, 8, 10, and 12 (on-treatment analysis)

Changes from baseline in morning pre-dose FEV1 at a specified visit will be calculated as follows:

*Morning pre-dose FEV1 at a specified visit – baseline FEV1.*

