### 3.6 Health economic and outcomes research assessments

The CAT is a validated, patient completed, questionnaire to measure the impact of COPD on a patient's health status. It is comprised of 8 questions to be answered independently by patient

via a paper questionnaire (See Appendix V of the CSP). Each question, except for total CAT score, ranges from 0 to 5 (5 indicates the worst health status). The total scores range from 0 to 40 (40 indicates the worst health status). Refer to Section 3.1.5.2 for scoring the CAT total score.

- Change from baseline in CAT score at visits 3, 4, 5, 6, 7, 8, 9, 10, 11, and 12

Changes from baseline in CAT score at a specified visit will be calculated as follows:

*CAT score at a specified visit – baseline CAT.*

- Proportion of patients with an improvement of 2 or more units from baseline in CAT total score at visits 3, 4, 5, 6, 7, 8, 9, 10, 11, and 12

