#### **Analyses for spirometry variable**

Change from baseline in morning pre-dose (trough) FEV1 by visit (on-treatment analysis) will be compared between aclidinium group and placebo using a MMRM model on patients with a baseline pre-dose/pre-bronchodilator FEV1 and at least one post-randomization pre-dose FEV1 in the FAS Population. The dependent variable will be the change from baseline in pre-dose FEV1 at postbaseline protocol-specified visits (up to Visit 12 or EOT visit). Treatment group will be fitted as the explanatory variable, and pre and post-bronchodilator (albuterol/salbutamol) FEV1 at screening visit (Visit 1A), and baseline FEV1 as covariates, and smoking status, baseline ICS use, visit, and treatment group-by-visit interaction as fixed effect factors. Visit will be fitted as a categorical variable, and the variance-covariance matrix will be assumed to be unstructured. Kenward Roger approximation will be used to estimate denominator degrees of freedom. If the procedure does not converge then a compound symmetric variance-covariance matrix will be used instead. The model is as follows:

*Change in FEV1 = treatment group + pre-bronchodilator FEV1 at Screening + post-bronchodilator FEV1 at Screening + baseline FEV1 + smoking status + Baseline ICS use + visit + treatment\*visit*

Each treatment effect and treatment difference between aclidinium and placebo at each visit will be estimated by their least squares (LS) means and the differences in LS means on the treatment-by-visit interaction, along with their standard errors (SEs), and 95% CIs and the p-value corresponding to the between-treatment-group difference. In addition, the overall treatment effect and treatment difference over the treatment period will be estimated by the LS means and the difference in LS means on the treatment factor, along with the SEs, and 95% CIs and the p-value corresponding to the between treatment group difference.

A longitudinal plot will be used to display the change from baseline in FEV1 at each visit by treatment group.

In addition, change from baseline in morning pre-dose (trough) FEV1 by visit (on-treatment analysis) will be analyzed for the following 2 subgroups:

- LABA users (with and without ICS)
- LABA/ICS users

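### If the unstructured MMRM does not converge, going straight to compound symmetry can make late-visit FEV1 and CAT confidence intervals too narrow (minor)

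*SAP*

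**What the plan says.** SAP section 4.2.4.3 (Analyses for spirometry variable) sets the first-choice model for FEV1: "Visit will be fitted as a categorical variable, and the variance-covariance matrix will be assumed to be unstructured". Inference is model-based: "Kenward Roger approximation will be used to estimate denominator degrees of freedom". The only provision for failure is "If the procedure does not converge then a compound symmetric variance-covariance matrix will be used instead". Section 4.2.6.1 repeats the same three rules for CAT total score.

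Both sections report the treatment difference at each visit with a standard error, 95% CI and p-value, and an overall difference across visits. Both also refit the model on two extracted subsets, LABA users and LABA/ICS users. No intermediate covariance structure and no empirical (sandwich) standard error is named.

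**The concern.** Compound symmetry is the most restrictive common choice. With 8 post-baseline FEV1 visits (section 3.4.2) and 10 CAT visits (section 3.6), the model falls from 36 or 55 covariance parameters to 2 in one step.

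Two features of long-term data could break it. Correlation between visits may weaken as they lie further apart, and the SD of change may drift over time. Kenward-Roger adjusts degrees of freedom and small-sample bias within the assumed covariance; it does not correct a wrong covariance. An error there passes directly into the by-visit intervals and p-values. With dropout, the assumed covariance also governs how early visits inform the missing late ones, so the estimates can shift as well.

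At stake is the stated precision of late-visit FEV1 and CAT differences, mainly in the subset analyses.

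**Working it through.** The SAP states no SD, correlation or interval width for FEV1 or CAT, so there is no figure of its own to reproduce.

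**Inputs from the SAP**
- Section 1.3.1: "a sample size of 4000 is needed to ensure 90% power to observe 122 events". Section 1.2 gives 1:1 allocation.
- Section 1.3.2: "The 89% power was calculated assuming a treatment discontinuation rate of 30% during the first year". Section 1.3.1 assumes 40% treatment discontinuation at year 2. Retention is therefore 70% at month 12 and 60% at month 24.
- FEV1 is analysed on treatment. Section 1.2 does not list CAT among the data collected after stopping treatment, so the same retention is used for CAT.

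**Assumptions not in the SAP**
- Retention at month 36: 50%, or 46% if the exponential rate implied by 40% at year 2 continues (0.6^1.5 = 0.465).
- A harsher case with retention of 70/45/20% at months 12/24/36. Section 1.3.1 needs 6,500 patient-years from 4,000 patients (6,500/4,000 = 1.6 years each), and 36 months is a maximum, so study closure may thin the late visits further.
- Visit months; true correlation constant (0.6), AR(1) with 0.6, 0.8 or 0.9 between adjacent visits, or a random intercept plus decay; SD constant, rising 20% or 50%, or falling 20% from first to last visit.

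**Parameter counts for T visits**
- Unstructured, T(T+1)/2: 36 for FEV1, 55 for CAT.
- Heterogeneous Toeplitz, 2T−1: 15 and 19.
- Heterogeneous AR(1), T+1: 9 and 11.
- Compound symmetry: 2.

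**Method**
1. For true covariance Σ and dropout patterns k with probability p_k, take the compound-symmetric W that minimises Σ_k p_k {log|W_k| + tr(W_k⁻¹Σ_k)}. This is what maximum likelihood converges to.
2. Set A = Σ_k p_k X_k'W_k⁻¹X_k and B = Σ_k p_k X_k'W_k⁻¹Σ_kW_k⁻¹X_k.
3. The model-based variance is proportional to A⁻¹ and the true variance to A⁻¹BA⁻¹. Sample size cancels in the ratio.
4. Let r = model SE / true SE. The CI width is wrong by the factor r, and coverage is 2Φ(1.96r) − 1.

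**Hand check with complete data.** Here the fitted variance is the mean of the visit variances. For 10 visits with SD rising linearly from 1 to 1.5, that mean is 1 + 2(0.5)(0.5) + 0.25(0.352) = 1.588, and its root is 1.260. So r = 1.260/1.5 = 0.84 at the last visit and 1.26 at the first, whatever the correlation.

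**Results at the last visit** (FEV1 and CAT give nearly the same ranges; rows with changing SD cover all correlation patterns)

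| Retention, months 12/24/36 | SD over visits | r | Coverage |
|---|---|---|---|
| 100/100/100% | constant | 1.00 | 95.0% |
| 100/100/100% | +20% | 0.92 | 92.8% |
| 100/100/100% | +50% | 0.84 | 90.0% |
| 100/100/100% | −20% | 1.13 | 97.3% |
| 70/60/50% | constant, constant correlation | 1.00 | 95.0% |
| 70/60/50% | constant, decaying correlation | 0.89–0.94 | 91.8–93.5% |
| 70/60/50% | +20% | 0.81–0.90 | 88.9–92.3% |
| 70/60/50% | +50% | 0.74–0.81 | 85.1–88.6% |
| 70/60/50% | −20% | 0.99–1.15 | 94.8–97.5% |
| 70/45/20% | constant, decaying correlation | 0.78–0.89 | 87.1–91.7% |
| 70/45/20% | +50% | 0.65–0.79 | 80.0–87.8% |
| 70/45/20% | −20% | 0.86–1.15 | 90.6–97.6% |

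A further run at about the plan's dropout gave r near 0.87 with constant SD and decaying correlation. Coverage is then 2Φ(1.96 × 0.87) − 1 = 2Φ(1.705) − 1 = 91%. With rising SD that run gave 0.71 to 0.77.

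**Other quantities, CAT, 70/60/50%.** The first-visit ratio is 1.00 to 1.01 with constant SD and 1.21 to 1.23 with SD up 50%. The overall treatment difference is nearly unaffected with constant SD (0.97 to 1.00) and ranges from 0.91 to 1.03 across the SD paths.

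**The case against.** A reader might infer that the rule makes late intervals far too narrow as a matter of course, and early ones too wide. The SAP does not support that. It states no SD or correlation pattern. With complete data and constant SD there is no error at all. With falling SD the last-visit interval is, at the plan's dropout, about right or too wide. The early excess width comes almost entirely from an assumed rise in SD.

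The trigger is also remote in the main analysis: about 4,000 patients should support 36 or 55 covariance parameters. The subsets are more exposed, since they have fewer patients, the same number of parameters and sparse late visits. The SAP gives no size for them, however, so no probability of failure can be stated.

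Nor is a confirmatory conclusion at risk. FEV1 is an additional efficacy variable and CAT a health-outcomes assessment. Neither is in the sequential order of section 4.2.4, which treats confidence intervals as descriptive.

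Finally, the SAP does fix a definite fallback in advance, and nothing is left open or contradicted. All of this stands, and it limits the size and importance of the point. It does not make compound symmetry with model-based standard errors a sound fallback once the first-choice model has failed.

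**Conclusion.** The point holds as a conditional and minor one. If the unstructured fit fails, the stated rule can give last-visit 95% CIs that are too narrow. At about the plan's discontinuation, with 46 to 50% retention at month 36 assumed, the shortfall is about 6 to 13% when correlation decays and SD is constant. A modest SD rise of 20% takes it to 10 to 19%, and the less favourable rising-SD scenarios to about 20 to 30%. With falling SD the interval is about right or too wide. Larger shortfalls, up to 35%, need both a steep SD rise and very low retention at the last visit. These are scenario results, not predictions from the SAP. No primary or secondary conclusion depends on them.

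**What to change.** In sections 4.2.4.3 and 4.2.6.1, replace the single fallback with an ordered list: heterogeneous Toeplitz, then heterogeneous AR(1), then compound symmetry last. State that any structured fallback is reported with empirical (sandwich) standard errors, and that the same order applies to the LABA and LABA/ICS fits.

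The cost is one sentence in each section, and nothing changes if the unstructured model converges. There are two drawbacks. Kenward-Roger is given up in the fallback, which matters little at about 4,000 patients; the empirical standard error is a large-sample method, so the subset sizes should be checked before relying on it. The empirical standard error also repairs only the variance: if compound symmetry is reached, the implicit prediction of missing late values still rests on it. That is why it should come last.

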#### **4.2.5 Safety analyses**

All safety analyses will be based on the FAS Population. No multiplicity adjustment will be made to CIs. All p-values will be unadjusted. The analyses of the secondary safety endpoint of the time to first MACE or other serious CV events of interest will not be adjusted for multiple comparisons.

#### 4.2.5.1 Primary safety variable

The null hypothesis is that treatment with acclidinium is inferior to treatment with placebo with regard to the risk of developing a MACE for a non-inferior (NI) margin of 1.8, i.e.:

$$H_0: \text{Hazard ratio (aclidinium over Placebo)} \geq 1.8$$

versus

$$H_a: \text{Hazard ratio (aclidinium over Placebo)} < 1.8$$

The primary safety variable of time to first MACE will be based on on-study analysis. Only events adjudicated by the Clinical Events Committee (CEC) will be included.

The primary safety variable of time to first MACE will be analyzed based on Cox-proportional hazards regression model including baseline CV severity, smoking status, and treatment group as covariates. The model is as follows:

$$\text{Time to first MACE} = \text{treatment group} + \text{baseline CV severity} + \text{smoking status}$$

This model will provide point estimate for the hazards ratio (aclidinium over placebo), as well as corresponding 95% CI and two-sided p-value (p-value will be presented for composite MACE endpoint only). The upper bound of the 95% CI (based on Cox regression) for the hazard ratio (aclidinium over placebo) of time to first MACE will be used to rule out the null hypothesis of hazard ratio of 1.8 for the primary test on MACE. If the upper bound of the 95% CI is less than the 1.8 margin of the hazard ratio, then the hazard ratio of 1.8 or higher will be ruled out (justification for the hazard ratio of 1.8 is provided in Appendix IV of the CSP).

In addition, the KM survival curves will be displayed for each treatment group.

To examine the contribution of the components of the composite endpoint to the overall treatment effect, time to first non-fatal MI, non-fatal stroke and CV death will be analyzed individually and presented in the same way as for the primary endpoint.

The results from the primary safety analysis will also be evaluated considering a superiority hypothesis.

#### Model assumption checking

The assumption of proportional hazards will be assessed visually using log-cumulative hazard plots. The effect of any departures from proportional hazards will be discussed as part of the presentation of results of the analyses.

#### Sensitivity analysis

To account for the relation of the occurrence of an event and treatment exposure, an on-treatment analysis will be conducted and this will include only events that occurred while the patient was exposed to study treatment, i.e., events that occurred after the patient's last

treatment dose will be censored. Two ascertainment windows, 0 and 15 days, will be evaluated in the on-treatment analyses. The on-treatment and on-treatment +15 days analyses will censor events that occur after and more than 15 days after, respectively, after the last treatment dose (see Section 9.7.6.1 of the CSP for consideration on totality of evidence from on-study and on-treatment analyses in evaluation of MACE).

To assess possible effects of informative censoring, sensitivity analysis (on-study analysis) will be done as follows: based on the missing follow-up time in drop-outs, i.e. the time from censoring to study closure, the expected number of events that might have been observed if the drop-outs had completed the study can be calculated using an event rate similar to that observed in the study. The test (aclidinium versus placebo) will be recalculated with these residual events allocated in different proportions to the treatment groups to assess the robustness of the results with regard to the censoring of drop-outs.

Sensitivity analysis of the primary composite endpoint will also include analysis with CV death replaced with all-cause mortality.

**Subgroup analysis.** To evaluate the consistency in the primary safety endpoint over selected baseline characteristics, subgroup analysis will be performed. The subgroup is described below:

- History of at least one exacerbation in the past year ( $0, \geq 1$ )

The subgroup analysis on time to first adjudicated MACE will be analyzed using the same method as the primary analysis on the primary safety endpoint using a 95% CI and without statistical testing for NI (NI margin will not be used).

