### **3.4 Additional efficacy variables**

#### **3.4.1 COPD exacerbation variables**

The following COPD exacerbation variables use data collected during the whole study period. Maximum follow-up time for a patient is approximately 36 months.

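### The informative-censoring sensitivity analysis for MACE counts missing follow-up all the way to study closure, although the SAP ends a patient's follow-up at about 36 months

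*SAP*

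**What the plan says.** SAP 4.2.5.1 (Sensitivity analysis) describes an on-study analysis of possible informative censoring. It starts from the follow-up that drop-outs are missing, defined as "the time from censoring to study closure". The aim is "the expected number of events that might have been observed if the drop-outs had completed the study", which "can be calculated using an event rate similar to that observed in the study". These residual events are then split between the arms in different proportions and the comparison is recalculated.

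Other sections bear on when a patient's follow-up ends:

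- SAP 3.4.1: "Maximum follow-up time for a patient is approximately 36 months". The variables introduced there use the whole study period, which SAP 1.2 defines as on-treatment plus post-treatment follow-up.
- SAP 1.2: the run-in is "followed by a maximum of 36-month double-blind treatment period".
- SAP 3.1.2: in on-study analyses, patients who completed treatment are censored at the end-of-treatment visit.
- SAP 3.5.7: vital status is collected at 3 years after randomization or when study completion is announced.
- SAP 4.2.1: when the study stops, some patients have completed 36 months of treatment or finished post-treatment follow-up. They are listed apart from those still on treatment or still in that follow-up.
- SAP 1.2, on patients who stop the product early: events are collected "for the remainder of the study duration".

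Closure is event-driven: "This study will conclude when 122 patients have experienced an adjudicated MACE".

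**The concern.** The definition does not match its own target. Under SAP 4.2.1 a patient can complete the study before it closes. Under SAP 3.1.2 a patient who completes treatment stops contributing at the end-of-treatment visit. A drop-out randomized on the same day as such a completer should therefore be credited with missing time only up to about 36 months, yet the rule runs on to closure.

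The surplus time becomes surplus residual events, and the direction of the distortion depends on how they are allocated. Placed mainly on aclidinium, they make the result look more fragile against the 1.8 margin than it is. Split evenly, they slightly narrow the confidence interval. What is at stake is how the robustness of the primary safety conclusion is read.

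**Working it through.** **1. Reproducing the plan's own figures (SAP 1.3.1).** Schoenfeld events for a margin of 1.8, two-sided 5%, 90% power, 1:1 allocation: 4 × (1.960 + 1.282)² / (ln 1.8)² = 121.7, so 122. Patient-years: 122 / 0.019 = 6,421, in line with the stated 6,500. Both reproduce.

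**2. One patient (illustrative dates).** Randomized 48 months before closure and dropped out at month 12. As written, missing time is 48 − 12 = 36 months. With follow-up ending at 36 months it is 36 − 12 = 24 months. The surplus, 12 months, is closure minus randomization minus 36 months.

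**3. Study level.** Inputs from SAP 1.3.1:
- N = 4000
- MACE rate λ = 0.019 per year
- study discontinuation 20% at year 2, exponential, so μ = −ln(0.8)/2 = 0.1116 per year
- closure where 122 events are expected (SAP 1.2)

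Assumed: uniform accrual, of several lengths, because the SAP gives none.

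For randomization at calendar time a, closure C and f = min(C − a, 3 years), the expected missing time is
- as written: ∫₀^f (C − a − t) μ e^{−(λ+μ)t} dt
- capped: ∫₀^f (f − t) μ e^{−(λ+μ)t} dt

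Averaged over a, multiplied by the number randomized, and then by 0.019:

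| Accrual (y) | Closure (y) | Missing patient-years, written / capped | Residual events, written / capped | Excess |
|---|---|---|---|---|
| 2 | 2.82 | 745 / 745 | 14.2 / 14.2 | 0% |
| 3 | 3.37 | 851 / 825 | 16.2 / 15.7 | 3% |
| 3.5 | 3.67 | 933 / 861 | 17.7 / 16.4 | 8% |
| 4 | 3.99 | 1,030 / 894 | 19.6 / 17.0 | 15% |
| 4.5 | 4.31 | 1,134 / 922 | 21.5 / 17.5 | 23% |

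Each row has about 716 drop-outs. In the last two rows closure comes at or before the end of accrual (about 3,833 randomized in the 4.5-year row), so they mark the upper end of the range.

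**4. Effect on the recalculated test (illustration).** Assume 61 observed events per arm and all residual events on aclidinium. The upper 95% limit is approximated by HR × exp(1.96 × √(1/a + 1/p)), where a and p are the aclidinium and placebo event counts and HR = a/p. For 4-year accrual:
- capped: a = 78.0, HR 1.279, upper limit 1.79
- as written: a = 80.6, HR 1.321, upper limit 1.84

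The limit reaches 1.8 at about 17.6 residual events, so the two definitions fall on either side of the margin. Split evenly, the upper limit moves only from 1.394 to 1.390.

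**The case against.** The strongest reply is that the plan may follow off-treatment patients to calendar closure. SAP 1.2 says their events are collected "for the remainder of the study duration", SAP 3.5.1.1 has adjudication run to the end of the study, and the explicit 36-month sentence sits under the exacerbation variables. On that reading the time is observable. The ambiguity is real, and it is why it would go too far to say that no event could ever be recorded in the surplus time. But that reading would follow patients who stopped the product for longer than those who completed it, and SAP 3.1.2, 3.4.1, 3.5.7 and 4.2.1 together point to an end at about 36 months.

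A second reply is that the stated target, read with the definition of completion in SAP 4.2.1, would lead a programmer to stop at the planned end of follow-up. That may happen, but the definition as written says otherwise.

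A third is size. With 122 events the event rate itself carries sampling error of about ±18% (1.96/√122), more than the excess for accrual of 4 years or less. That stands as a reason to rank the point low. The crossing of 1.8 shown above also needs long accrual, equal observed events and the most extreme allocation at once.

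A reader might infer larger effects by choosing closure dates freely. For example, 2.5 years of accrual with closure at 4 years gives 29.7 against 25.5 events (+17%), and 3 years with closure at 4.2 years gives 29.3 against 24.2 (+21%). The SAP does not support those cases with 4000 patients: they imply about 164 and 159 MACE, well past the 122 at which the study ends.

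**Conclusion.** The point holds as a mismatch between a stated rule and its stated target. For drop-outs randomized more than 36 months before closure, residual events are overcounted. Under the SAP's planning inputs and its 122-event closure rule, the excess runs from nothing (2 years of accrual) through about 3% (3 years), 8% (3.5 years) and 15% (4 years) to 23% (4.5 years). This rests on uniform accrual of assumed length, exponential drop-out, and follow-up ending 36 months after randomization.

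The consequence is confined to one sensitivity analysis. A reader might infer that the primary safety result is miscalibrated. It is not: the primary test, the margin, the 122 events and the power do not use this quantity. The crossing of the 1.8 margin shows that the definition can decide how an extreme allocation reads; it does not predict that it will. This is a minor correction worth making.

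**What to change.** In SAP 4.2.5.1, define a drop-out's missing follow-up as running from the censoring date to whichever comes first: study closure or the patient's planned end of follow-up, 36 months after randomization. In the same edit, say in SAP 1.2 when post-treatment follow-up ends, so that it agrees with SAP 3.4.1, 3.5.7 and 4.2.1. If the sponsor does intend off-treatment follow-up to run to calendar closure, those three sections need changing instead, and the end-of-treatment censoring of completers in SAP 3.1.2 should be reconciled with that.

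The cost is one phrase in the sensitivity analysis and one clarifying sentence. No new data are needed and the primary analysis does not change.
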